The primary aim of this substudy is to use bioimpedance spectroscopy to assess, in a subset of EMPA-KIDNEY participants, the effect of empagliflozin 10mg versus matching placebo on "Fluid Overload" at the 2 month and 18 month Follow-up Visits.

Secondary aims are to use bioimpedance spectroscopy to assess:

- 1. Whether any effects of empagliflozin 10mg versus matching placebo on "Fluid Overload" are modified by baseline factors, in particular by level of kidney function, glycosylated haemoglobin, body mass index, NT-proBNP, age, sex, RAS inhibitor use, and different diuretics
- 2. The effects of empagliflozin 10mg versus matching placebo early and later during follow-up on:
 - o ECW
 - Intracellular water (ICW)
 - Adipose tissue mass indexed to weight (i.e. %)
 - Lean tissue mass indexed to weight (i.e. %)

Exploratory aims are to:

 Assess if changes in ECW, ICW, % adipose tissue mass, % lean tissue mass and "Fluid Overload" correlate with changes in blood pressure and relevant other biomarkers.

Sample size estimates

The study will start a vanguard phase in a small number of sites in which bioimpedance spectroscopy will be performed at Randomization, 2 months and 18 months of Follow-up Visits. This vanguard phase will be expanded to other sites once feasiblity of adding a bioimpedance spectroscopy measurement is demonstrated. Feasiblity will be based on feedback from the participating sites, successful completion of the other protocol-specified procedures and logistical considerations. It is estimated that at least 400 (of the 5000) EMPA-KIDNEY participants with follow-up bioimpedance spectroscopy measurements will provide ample power (>90%, 2p=0.05) to detect at least a ±300mL difference in "Fluid Overload" (reference range in healthy adults is ± 1100mL with a standard deviation of 900mL) based on an independent 2-sided t-test (Table 1).

Table 1: Sample size calculations for a study with Randomization Visit measurements

Outcome	Effect size	Standard deviation	Required sample size
"Fluid Overload" (ref range: ±1.1L)	±300mL	900mL	382

Note: An estimate of the correlation between successive bioimpedance spectroscopy measurements would be required to calculate the reduction in sample size that could be achieved by using ANCOVA analyses, but no such longitudinal data has yet been collected in a CKD population.

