If a bioimpedance spectroscopy measurement at the Randomization Visit is shown to be infeasible, the substudy will be modifed to exclude the measurement at the Randomization Visit and only be performed at the relatively less busy phases of the study (i.e. measurements will be restricted to the 2 and 18 month Follow-up Visits). In this design, the sample size would need to increase to 850. This is because the absence of a bioimpedance spectroscopy measurement at the Randomization Visit means any imbalances in "Fluid Overload" between treatment arms at baseline cannot be corrected for. These imbalances could result in either the treatment effect being overestimated or a smaller than expected difference in mean "Fluid Overload" at follow-up. However, with a sample size of 850, the probability of large baseline imbalances is small, making it unlikely that the treatment effect would be overstated by more than 100mL (Table 2). With a sample size of 850, there would be sufficient power to detect a reduced difference in mean "Fluid Overload" of ± 200 mL at follow-up. This calculation is based on an independent 2-sided t-test using data from a healthy population (Note: sample size estimates differ little if dialysis population data are used).

[figure not shown]
Table 2: Sample size calculations for a study without Randomization Visit measurements

Sample size	Assumed possible baseline imbalance in Fluid Overload (mL)	Probability of a baseline imbalance at least this size due to chance (1-sided)	Difference between groups at follow-up (mL) after subtracting possible baseline imbalance from assumed treatment effect of 300 mL	Power to detect reduced difference in follow-up values at 2p=0.05
850				
	0	Not applicable	300	>99%
	50	12.6%	250	98%
	100	1.1%	200	90%
	150	0.03%	150	68%
	200	0.0002%	100	37%

Data Analysis Plan

The primary analysis will estimate the differences in "Fluid Overload" between treatment groups across all time points, regardless of whether a participant received all, some or none of their allocated treatment (i.e. intention-to-treat analyses). Secondary outcomes include ECW, ICW, % adipose tissue mass, and % lean tissue mass". Differences in "Fluid Overload" and the secondary outcomes between treatment groups overall, and separately at 2 and 18 months, will be calculated using linear regression adjusted (or stratified) for the elements included in the minimization

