algorithm. The primary analysis will focus on a weighted average of the values at the two time points (with weights proportional to the amount of time between visits). Missing measurements will be imputed. Results from the imputed analyses will be compared with those from equivalent "complete-case" analyses, but primary emphasis will be placed on the results after multiple imputation. More complete details of statistical methods, including definitions of subgroups, methods of imputation, approaches to adjustments and weighting of averages will be set out in a separate full Data Analysis Plan which will be consistent with the main study Data Analysis Plan.

Flowchart of Substudy Activities

INVITATION

- Invite potential participants shortly before or at the time of the Randomization Visit
- Written informed consent is sought from willing individuals at the first visit when a bioimpedance spectroscopy measurement is offered

RANDOMIZATION VISIT AND AT 2 & 18 MONTHS OF FOLLOW-UP

 A bioimpedance spectroscopy measurement is added to the protocol-specified study follow-up visit procedures

Design

Eligibility: In selected regions, EMPA-KIDNEY Local Clinical Centres (LCCs) with a Fresenius Medical Care Body Composition Monitor (BCM) machine will be invited to join this optional substudy. All those participants at these LCCs who have yet to attend the relevant scheduled study visit are eligible for invitation. There are no exclusion criteria.

Invitation and methods: Potential participants will be invited to join this substudy at before or around the time of their Randomization Visit. At the relevant visit, clinic staff will explain the substudy to potential participants using the Participant Information Leaflet and Consent Form. Consenting participants will have a measure of bioimpedance made in addition to the protocol-specified follow-up procedures. Bioimpedance measurements take about 2 minutes to record and pose no risk to health (although it is conceivable the 4 self-adhesive pads could rarely cause a skin reaction).

Body Composition Measurement

Training materials on how to perform Body Composition Measurements will be provided. The measurement requires

EMPA-KIDNEY Body composition measurement substudy justifi V1.0 – 02-MAR-2019

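### The named regression adjusts only for the minimization elements, although the sample-size argument implies that a measured baseline Fluid Overload would be corrected for

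*Protocol*

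**What the plan says.** In the default design, bioimpedance is measured at Randomization, 2 months and 18 months, with at least 400 participants (Protocol, Sample size estimates). The fallback opens with "If a bioimpedance spectroscopy measurement at the Randomization Visit is shown to be infeasible": that visit's measurement is then dropped and the sample rises to 850. The reason given is that imbalances in Fluid Overload "between treatment arms at baseline cannot be corrected for". The text adds: "These imbalances could result in either the treatment effect being overestimated or a smaller than expected difference in mean" Fluid Overload at follow-up.

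The Data Analysis Plan section of the protocol then names one model for Fluid Overload and the secondary outcomes. Differences "will be calculated using linear regression adjusted (or stratified) for the elements included in the minimization" algorithm. On the outcome it says: "The primary analysis will focus on a weighted average of the values at the two time points", so the analysis uses follow-up values and not change from baseline. The sentence does not distinguish the two designs.

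Two passages bear on whether a baseline term is intended. The note to Table 1 refers to "the reduction in sample size that could be achieved by using ANCOVA analyses" but says the correlation needed to size that gain is not available. The Data Analysis Plan section ends by saying that "approaches to adjustments and weighting of averages will be set out in a separate full Data Analysis Plan".

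**The concern.** The inability to correct for baseline can separate the 850 design from the 400 design only if the 400 design does make that correction. The one adjustment the protocol names would not make it. The minimization elements are not listed in this document, but baseline bioimpedance can hardly be among them: the substudy is optional, covers a subset of participants and leaves the main protocol unchanged.

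At stake is the precision of the primary and secondary estimates in the default design. The baseline value of an outcome is often its strongest predictor, and here it is already collected. Leaving it out gives a wider interval and, in any one trial, an estimate that carries part of whatever baseline imbalance chance has produced. These are one harm seen in two ways, because the standard error of the analysis without baseline already averages over chance imbalance.

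**Working it through.** **1. The protocol's own figure.** Inputs from Table 1: difference 300 mL, SD 900 mL, two-sided 0.05, 90% power, independent t-test. Allocation 1:1 is assumed; it reproduces the table. The t-test needs 191 per arm, 382 in total (power 90.1%). N=400 gives 91.4%. No baseline term enters, so the stated size does not depend on one.

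**2. Chance imbalance at N=400.** The SE of the baseline difference is 900 × √(2/200) = 90 mL. The one-sided chance of an imbalance of at least 100 mL is P(Z > 100/90) = 13.3%, or 26.7% in either direction. This is before any adjustment for the minimization elements. If those explain 20% of the variance, the SE of the remaining imbalance is 90 × √0.8 = 80.5 mL and the one-sided chance is about 10.7%.

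**3. What the baseline term would gain.** Assumptions, none of them given in the protocol:
- ρ: correlation between any two visits, equal for all pairs; 0.3, 0.5 and 0.7.
- R²: share of Fluid Overload variance explained by the minimization elements, the same at every visit and through the same linear predictor; 0, 0.1 and 0.2. R² = 0 is an upper-end illustration of the gain.
- Weights: time-proportional, 2/18 = 1/9 at 2 months and 16/18 = 8/9 at 18 months. The protocol leaves the exact weighting to the separate plan.

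Formulas, with V = (1/9)² + (8/9)² + 2(1/9)(8/9)ρ:
- SE, minimization elements only: 90 × √(V − R²)
- SE, plus baseline: 90 × √(V − R² − (ρ − R²)²/(1 − R²))
- Shift in the estimate per mL of imbalance remaining after the minimization elements: (ρ − R²)/(1 − R²)

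Example, ρ = 0.5 and R² = 0.2: V = 0.901. Without baseline, 90 × √0.701 = 75.4 mL. With baseline, 90 × √(0.701 − 0.09/0.8) = 69.1 mL. A simulation of 6,000 trials gave 75.3 and 69.3 mL.

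| R² | ρ | SE without baseline (mL) | SE with baseline (mL) | Variance cut | Shift per 100 mL |
|---|---|---|---|---|---|
| 0 | 0.3 | 83.5 | 79.1 | 10% | 30 mL |
| 0 | 0.5 | 85.4 | 72.6 | 28% | 50 mL |
| 0 | 0.7 | 87.3 | 60.4 | 52% | 70 mL |
| 0.1 | 0.3 | 78.5 | 76.2 | 6% | 22 mL |
| 0.1 | 0.5 | 80.6 | 71.1 | 22% | 44 mL |
| 0.1 | 0.7 | 82.5 | 59.7 | 48% | 67 mL |
| 0.2 | 0.3 | 73.2 | 72.5 | 2% | 13 mL |
| 0.2 | 0.5 | 75.4 | 69.1 | 16% | 38 mL |
| 0.2 | 0.7 | 77.5 | 58.9 | 42% | 63 mL |

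**4. Detectable difference.** With 90% power (normal approximation) it is 3.2415 × SE. At ρ = 0.5 it falls from 277 to 235 mL (R² = 0), from 261 to 230 mL (R² = 0.1) and from 244 to 224 mL (R² = 0.2).

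**5. Sensitivity.** With equal weights and R² = 0.2, the SE falls from 60.4 to 59.5 mL (ρ = 0.3), 66.7 to 59.5 mL (ρ = 0.5) and 72.6 to 52.3 mL (ρ = 0.7), so the direction does not depend on the weights. If the correlation fades with time (baseline with 2 months 0.5, baseline with 18 months 0.3, between follow-ups 0.3), the variance cut is about 3% at R² = 0.2 and 12% at R² = 0.

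**The case against.** The strongest reply is that the protocol expressly leaves approaches to adjustment, and methods of imputation, to a separate plan that is not available here. The regression sentence does not say that only the minimization elements will be used. The Table 1 note raises ANCOVA, and the sample-size text treats correction as possible when a baseline exists. On this reading one short sentence gives the adjustment common to both designs, written before the vanguard phase had settled which would apply. Nothing in the 382 or 400 depends on baseline adjustment.

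Much of this stands. The document does not show that the final analysis omits baseline, and no stated figure is wrong. The size of the gain rests on assumed correlations, and the equal-correlation assumption is favourable: under the fading pattern the cut is 3% to 12%, within the range above but towards its lower end.

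What remains is that the protocol does more than stay silent. It names an adjustment set, and that set does not match its own reason for separating 400 from 850. ANCOVA appears only as a possible saving, not as the planned analysis. A separate plan could follow the named model literally, comply with the protocol, and leave out the correction.

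**Conclusion.** The point holds as an improvement available at no cost, not as an error in power, sample size or validity. As named, the regression would not make the baseline correction that the comparison of 400 with 850 participants relies on. At N=400, with SD 900 mL and 1:1 allocation, adding the baseline value would reduce the variance of the primary estimate by between 2% and 52% over the assumed ranges. The gain depends mainly on how strongly baseline predicts the 18-month value, which the protocol says is unknown in a CKD population. The same sentence governs the secondary outcomes, but the document has no figures from which to size the gain there. Confidence is medium, because the separate full Data Analysis Plan may already include the term.

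**What to change.** State in the Data Analysis Plan section of the protocol that, where the Randomization Visit measurement is made, the primary and secondary models adjust for the baseline value of the same bioimpedance measure in addition to the minimization elements, and that this value enters the imputation model. Keep the minimization elements alone for the fallback design without that measurement. If the separate plan already says this, only the protocol sentence needs aligning.

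The cost is one sentence. The default design already collects the measurement, so no data, visits or participants are added. Fixing the covariate in advance also removes a later choice made with results in view.

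### Does weighting the 2- and 18-month values by the time between visits turn the primary result into little more than an 18-month effect, so that the weights must change?

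*Protocol*

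**What the plan says.** The primary aim (Aims section) is the effect of empagliflozin on fluid overload "at the 2 month and 18 month Follow-up Visits". Under Sample size estimates, bioimpedance is to be "performed at Randomization, 2 months and 18 months of Follow-up Visits". In the fallback design, "measurements will be restricted to the 2 and 18 month Follow-up Visits".

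The Data Analysis Plan section then says: "The primary analysis will focus on a weighted average of the values at the two time points", and adds in brackets "with weights proportional to the amount of time between visits". It gives no numeric weights. Two further statements matter here. Differences are to be calculated "between treatment groups overall, and separately at 2 and 18 months". And "approaches to adjustments and weighting of averages will be set out in a separate full Data Analysis Plan", which is to be consistent with the main study's plan. That separate document is not at hand.

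**The concern.** A rule that weights by interval does little harm when visits are many and evenly spaced. Here there are two follow-up visits, and the gaps before them are 2 and 16 months. If each value is weighted by the gap that precedes it, month 18 receives eight times the weight of month 2, as if the 18-month difference had applied from just after month 2.

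Three things seem to be at stake. The primary result would fit poorly with an aim that names both visits. Much of the precision gained from measuring twice would be lost. And a fluid effect that is larger early than late would be reported as much smaller than under an average that joins the two visits by a straight line.

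**Working it through.** **Inputs.** Visit times 0, 2 and 18 months, effect 300 mL, SD 900 mL, two-sided 5% and at least 400 participants come from Sample size estimates and Table 1. Equal allocation is assumed. The correlation r between the 2- and 18-month values is not given (the note to Table 1 says no such longitudinal data exist in CKD), so a range is used.

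**The plan's own figure.** A two-sample t-test with 300/900, two-sided 5% and 90% power needs 380.2 in total, or 190.1 per arm. Rounded up to 191 per arm this is 382, as in Table 1. The calculation uses one measurement per person and claims no gain from averaging.

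**Weights the phrase can give.**
- Interval before each visit: 2/18 = 11.1% and 16/18 = 88.9%.
- Time nearest to each visit over 0–18 months (boundary at month 10): 10/18 = 55.6% and 8/18 = 44.4%.
- Straight line over months 2–18: 50% and 50%.
- Straight line over 0–18 months: baseline 1/18, month 2 9/18, month 18 8/18. Dropping baseline and rescaling gives 9/17 = 52.9% and 8/17 = 47.1%.

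**Effect on the estimate** (assumed true differences, mL):

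| Month 2, month 18 | 2:16 | 9:8 | 1:1 |
|---|---|---|---|
| 300, 300 | 300 | 300 | 300 |
| 300, 150 | 166.7 | 229.4 | 225 |
| 300, 100 | 122.2 | 205.9 | 200 |
| 150, 300 | 283.3 | 220.6 | 225 |

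**Which is the true time average?** Take 300 mL at month 2 and 100 mL at month 18.
- Straight lines from zero at baseline: (2 × 150 + 16 × 200)/18 = 3500/18 = 194 mL.
- Straight line over months 2–18 only: 200 mL.
- 300 mL held over months 0–2, then a straight line: (600 + 3200)/18 = 211 mL.
- 300 mL up to month 2, then a plateau at 100 mL: (2 × 300 + 16 × 100)/18 = 122 mL.

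The last course is reproduced exactly by 2:16. None of the four equals the 206 mL that 9:8 gives.

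**Variance relative to one visit**, w1² + w2² + 2·w1·w2·r, for r = 0.5, 0.7, 0.8:
- 2:16: (65 + 16r)/81 = 0.901, 0.941, 0.960.
- 9:8: (145 + 144r)/289 = 0.751, 0.851, 0.900.

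The ratios are 1.20, 1.11 and 1.07, so 2:16 carries 20%, 11% or 7% more variance.

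**Power for a constant 300 mL, 200 per arm**, Φ(300/(SDw·√(2/200)) − 1.96), where SDw is 900 times the square root of the variance factor:

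| r | SDw, 2:16 | Power, 2:16 | SDw, 1:1 | Power, 1:1 |
|---|---|---|---|---|
| 0.3 | 835 | 94.9% | 726 | 98.5% |
| 0.5 | 854 | 94.0% | 779 | 97.1% |
| 0.7 | 873 | 93.0% | 830 | 95.1% |
| 0.9 | 891 | 92.0% | 877 | 92.8% |

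One visit alone gives 91.5%, so 2:16 does no worse than the design assumed.

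**Power when the effect changes**, r from 0.3 to 0.9:
- 300 falling to 150 mL: 46–51% under 2:16, 73–87% under 1:1.
- 150 rising to 300 mL: under 2:16, 283.3/83.5 − 1.96 = 1.43 (92%) to 283.3/89.1 − 1.96 = 1.22 (89%). Under 1:1 it is again 73–87%, because the average is again 225 mL.

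**The case for a change.** The strongest case for a change is that this is more than missing detail. The protocol already states a weighting principle, so the separate plan must either follow it, at about 11% and 89%, or reinterpret it. Because the phrase can also be read as 56/44 or 50/50, the primary estimate is not uniquely defined by this document. The loss is real if the effect wanes: about half the trials would miss a fall from 300 to 150 mL under 2:16. Nothing in the text says that a late emphasis was intended. The later visit would also ordinarily carry more missing data, so the primary result could lean more on imputation.

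Part of this stands. The 2:16 split is the most natural reading, it yields mainly an 18-month effect, and the numbers ought to be settled before anyone sees unblinded data. But that is what the separate plan is assigned to do. The waning case has a mirror image in which 2:16 gains, and nothing in the document says which is likelier for fluid overload. The document gives no missingness rates, and it already plans multiple imputation with a complete-case comparison. Finally, the 9:8 replacement has no special claim: it does not match the 194 mL straight-line average used to justify it, and equal weights would serve about as well, so the choice is one of emphasis.

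**Conclusion.** No change follows. Any weights fixed in advance give a valid randomised comparison. They differ in which effect they summarise, and only when the effect differs between the visits. Interval weighting is a time average under a step-shaped time course; straight-line weighting is a time average under another assumption, made across 16 months with no bioimpedance measurement. Favouring the sustained effect is a fair choice, and the separate 2- and 18-month estimates show a reader both effects named in the primary aim whatever the overall weights are.

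The cost of 2:16 is modest under a constant effect: 7 to 20% more variance than 9:8 for assumed correlations of 0.8 down to 0.5, with power still at 92 to 95% for 300 mL and 400 participants. Those power figures assume equal allocation and SD 900 mL, with no gain from baseline adjustment, as in Table 1. Moving to near-even weights would shift the primary question from mainly late to evenly early and late, and might break consistency with the main study's plan, which cannot be seen here. What remains is that numeric weights are not written in this document. That is detail it assigns to the separate plan, and analysts would be expected to fill it in there.
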